6. STUDY ENDPOINTS

6.1. Primary Safety Endpoint

The rate of occurrence of each arm of clinically significant serious adverse events defined as:

- Serious infection (urosepsis, pyelonephritis) requiring hospitalization and treatment through 90 days post index procedure
- New urinary tract stricture formation requiring surgical intervention through 90 days post index procedure

Confidence intervals will be presented to aid in the evaluation of the incidence of clinically significant serious adverse events, both for each treatment group individually, and for the difference in the rates between the two treatment groups.

6.2. Primary Efficacy Endpoint

Treatment success: Proportion of study subjects who have a complete absence of stone(s), or have residual fragments measuring to ≤ 2 mm, as assessed by CT imaging through 30 days follow-up post index procedure. CT imaging will be assessed by an independent core lab to determine treatment success. Treatment success, as defined by an absence of residual fragments >2mm on any dimension, has been identified as a priority in stone care in recent publications including Margaret Pearle's widely cited "Is Ureteroscopy as Good as We Think", published in the Journal of Urology in 2016 [12]. Increasing awareness and clinical prioritization of residual fragments in ureteroscopic laser lithotripsy derives in large part from expanded use of CT follow-up imaging in stone subjects. CT imaging has allowed characterization of residual fragments and full appreciation of their clinical significance, with rigorous studies of residual fragment natural history having established a 2mm threshold as a critical size above which additional stone events are particularly frequent [22], [23]. Therefore, the primary efficacy endpoint will demonstrate that the investigational arm (Acoustic Enhancer +_URS-LL) is superior in the fragmentation of stones to $\leq 2mm$ versus the control arm (URS-LL).

6.3. Secondary Efficacy Endpoint

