11.1. Adverse Event

An adverse event (AE) is any undesired clinical response or complication experienced by a subject. Monitoring and documenting of adverse events will begin at the start of the index procedure. When an adverse event is recorded as ongoing, an effort will be made to follow-up on the event at subsequent subject visits until the event is resolved or the subject exits the study.

CONFIDENTIAL Page 36 of 53

In this study, adverse events should be reported beginning at the time of administration of general anesthesia for the index procedure. Pre-existing conditions (recorded on the Medical History CRF), which occur during the study at the same severity as in the subject's history, should not be recorded as adverse events. Pre-existing conditions (recorded on the Medical History CRF) that worsen during the study OR a new episode begins must be recorded as AE(s). The onset date should be the start of the current episode or the date of the change in severity, not the onset date recorded on the Medical History CRF.

Upon enrollment, if a new adverse event is reported and subsequently determined to be medical history not previously documented, the information should be added to the medical history CRF. The event should be recorded as an AE only if there was a change in severity.

Intermittent Events

An AE that occurs intermittently at the same severity should be aggregated and recorded as one event unless, in the opinion of the Investigator, the events should be reported as discrete events (medical diagnosis terms).

- The onset date is the start of the first episode during the study.
- The resolution date is the end of the last episode (or may be persistent, if ongoing at the end of the study).
- The site should record "intermittent" in the AE description. If an intermittent event meets the regulatory criteria for seriousness, the associated frequency of the adverse event term (e.g., 4x/week) should be captured in the narrative/comment section of the CRF.
- If the event changes in severity or relationship to study device, it should be recorded as an AE update.

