4. Definitely related: The adverse event is clearly caused by the use of the device, device malfunction, or the procedure. It must meet all following criteria: (1) has a clear temporal relationship between device exposure and onset of the event; (2) follows a known pattern of response to device use or procedure; and (3) is not reasonably attributable to the underlying disease, disorder or condition of the subject, or attributable to other extraneous causes.

Severity of an AE will be determined by the Investigator following Common Terminology Criteria for Adverse Events (CTCAE):

Grade 1: Mild; asymptomatic or mild symptoms; clinical or diagnostic observations only; intervention not indicated.

Grade 2: Moderate; minimal, local or noninvasive intervention indicated; limiting age appropriate instrumental Activities of Daily Living (ADL)*.

Grade 3: Severe or medically significant but not immediately life-threatening; hospitalization or prolongation of hospitalization indicated; disabling; limiting self-care ADL**.

Grade 4: Life-threatening consequences; urgent intervention indicated.

Grade 5: Death related to AE.

Note: *Instrumental ADL refer to preparing meals, shopping for groceries or clothes, using the telephone, managing money, etc.

**Self care ADL refer to bathing, dressing and undressing, feeding self, using the toilet, taking medications, and not bedridden.

The term "severe" is used to describe intensity (severity) of a specific event. An event itself, may be of relatively minor medical significance (such as a severe headache). This is not the same as "serious", which is based on subject/event outcomes or action criteria usually associated with events that pose a threat to the subject's life or functioning.

For the purposes of safety reporting in this study, the following definitions will be applied:

- An **Adverse Event** (AE) is any untoward medical occurrence in a subject whether it is considered device related or not. Diseases, signs, symptoms, or laboratory abnormalities already existing at enrollment are not considered AE's unless they worsen (i.e., increase in intensity or frequency). Surgical procedures themselves are not adverse events; they are therapeutic measures for conditions that require surgery. The condition for which the surgery is required may be an adverse event. Surgical procedures planned prior to enrollment and the conditions leading to these measures are not adverse events.

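### Protocol 11.1 gives inconsistent triggers for recording a pre-existing condition as an adverse event, and the rule for late-found history omits a new episode (minor)

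*Protocol*

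**What the plan says.** Protocol Section 11.1 (Adverse Event) contains four statements on conditions that pre-date the procedure.

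1. Documented history, same severity. Conditions on the Medical History form "which occur during the study at the same severity as in the subject's history, should not be recorded as adverse events".
2. Documented history, worsening or new episode. The next sentence says that such conditions, if they worsen or start a new episode, "must be recorded as AE(s). The onset date should be the start of the current episode or the date of the change in severity".
3. Late-found history. If a reported event is "subsequently determined to be medical history not previously documented, the information should be added to the medical history CRF". The rule then adds: "The event should be recorded as an AE only if there was a change in severity".
4. AE definition, later in the same section. Conditions existing at enrollment are not AEs "unless they worsen (i.e., increase in intensity or frequency".

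Section 11.1 also defines an SAE as an AE that meets a seriousness criterion, hospitalization among them. One component of the primary safety endpoint in Section 6.1 is "Serious infection (urosepsis, pyelonephritis) requiring hospitalization and treatment through 90 days post index procedure".

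**The concern.** The four statements do not share a trigger. Statement 2 counts a new episode, statement 3 does not, and statement 4 adds frequency. Statement 1, read alone, would exclude the same-severity recurrence that statement 2 requires to be recorded.

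The late-found rule matters most, because its word 'only' makes severity the sole criterion. Two subjects with the same post-procedure event could be handled differently according to how complete the history form was at screening. An event not recorded as an AE cannot be an SAE, so it would not prompt the 24-hour report in Section 11.1 or enter the AE tables in SAP Section 9.2.

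The judgement that an event is history comes after the event, and Section 11.1 does not say who makes it. Blinding under Protocol Section 7.4 covers the subject and the CT reader. The operator knows the arm, and SAP Section 12 plans no data safety monitoring board activity.

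**Working it through.** No arithmetic settles this. The check sets the rules side by side and follows one case through them.

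**Rules in Protocol Section 11.1, taken literally**

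| Rule | Greater severity | Greater frequency, same severity | New episode, same severity |
|---|---|---|---|
| 1. Documented, same-severity sentence | not excluded | not recorded | not recorded |
| 2. Documented, following sentence | record | not named | record |
| 3. Late-found history | record | not recorded | not recorded |
| 4. AE definition | record | record | not named |

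The onset-date instruction attached to rule 2 allows either the start of the current episode or the date of the severity change. Rule 2 therefore treats these as two separate triggers, and leaving one out of rule 3 makes a real difference.

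**One case**

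Take a subject with an earlier hospitalized pyelonephritis of Grade 3 who is admitted after the procedure with a new Grade 3 pyelonephritis.

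- Can such a subject enrol? Yes. Sections 5.8.9 and 5.8.10 exclude untreated urinary infection and a history of drug-resistant chronic infection, not a past pyelonephritis.
- Can severity be unchanged? Yes. Grade 3 in Section 11.1 includes events for which hospitalization is indicated, so both episodes can carry that grade.
- Earlier episode on the form: rule 2 applies and the new episode is recorded. Rule 1 alone would say the opposite.
- Earlier episode missing from the form, and the new event then classed as history: under rule 3 severity has not changed, so it is not recorded.
- Is it an endpoint event? Yes, by the Section 6.1 definition.

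**Does other text close the gap?**

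- Section 11 (opening paragraph) requires all procedural and post-procedural complications to be recorded. This favours recording and so conflicts with a literal rule 3.
- Section 11.1 also requires all peri- and post-procedural AEs to be recorded. This does not help, because whether the event is an AE is the open question.
- The SAP table list (Section 14.1) has no separate primary safety table. SAP Section 4 refers primary and secondary endpoint assessments to another plan, so this review cannot tell whether that plan would identify the event by another route.

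**Scale**

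With 196/2 = 98 subjects per arm, one event is 1/98 = 1.0 percentage point of an arm's rate. That is true of any event and does not estimate how many would be missed.

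**The case against.** The strongest reply is that rule 3 covers something else. It applies when the event itself is found to be history, and its paragraph opens by referring to enrollment, which Sections 5.4 and 7.5 define as signing consent. Its natural subject is a condition missed at history-taking, not an infection that starts after anesthesia. Rule 3 also first orders the condition onto the Medical History form, after which rule 2 arguably applies and requires a new episode to be recorded. A resolved past infection does not exist at enrollment, so the carve-out in the AE definition does not reach it. The example is also narrow: it needs a comparable earlier episode missed at screening, plus a decision to class a new admission as history. There is some oversight too. An independent medical monitor reviews safety data (Section 13), and study monitors check AEs and unscheduled visits against source (Section 12.2).

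Most of this stands, and it is why the point is minor. The mismatch remains: rule 3 is a specific instruction for that very event, and a coordinator working through the paragraph in order could stop there.

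A reader might infer more than the documents support in three ways.

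- **That the protocol as a whole drops these events.** It does not. Section 11 and rule 2 point towards recording.
- **That hydronephrosis capture is equally exposed.** Hydronephrosis is not in the primary safety endpoint. The Day 90 rule (Sections 5.6 and 8.5) already names pre-existing hydronephrosis that worsened or recurred. The stricture component of the endpoint is limited to new strictures.
- **That one missed event would remove a known share of the expected count.** Section 9.1 gives 2% to 10% for kidney injury or infection needing further treatment, or 0.02 × 98 = 2.0 to 0.10 × 98 = 9.8 subjects per arm. One event would then be 1/9.8 = 10% to 1/2.0 = 51% of that count. But the class is broader than the endpoint, and the probability of a miss is not given, so these figures say nothing about the expected loss.

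**Conclusion.** The recording triggers in Protocol Section 11.1 are inconsistent and should be reconciled. Under a literal reading of the late-found-history sentence, a same-severity new episode after the procedure could go unrecorded as an AE, and so as an SAE. This includes an event that meets the primary safety definition. Because other text favours recording, it is a risk under one reading.

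The size cannot be estimated: the documents do not say how often history is undocumented or how often such conditions recur at the same grade. The history form is completed at screening, before randomization, so its completeness should be balanced between arms in expectation. An imbalance would need the later classification to depend on the arm, and nothing in the documents shows that it would. Severity is minor. The primary efficacy analysis is not affected.

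**What to change.** Amend Protocol Section 11.1 and any form-completion instructions that repeat it:

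- **Late-found history.** Add the condition to the Medical History form, and record the event as an AE if severity or frequency increased or a new episode began at or after administration of general anesthesia. Use the same triggers for documented history.
- **Same-severity sentence.** Limit it to conditions that continue unchanged at the same severity, so that it no longer conflicts with the new-episode rule.
- **Backstop.** State that an event with onset at or after anesthesia that meets an SAE criterion or a primary safety definition is recorded regardless of history. Keep the existing exceptions in Section 11.1 for procedures planned before enrollment and the conditions leading to them, and for planned hospitalizations. Without them the backstop would create a new contradiction.

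The cost is two or three sentences and slightly more AE records in both arms. No change to the sample size or efficacy analysis is needed.

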11.2. Device Malfunction

For the purposes of this protocol, a device malfunction is defined as the failure of a device to meet its performance specifications or otherwise perform as intended [21CFR803.3(k)]. Examples of a device malfunction include breached packaging, broken Acoustic Enhancer vials.

All device malfunctions must be reported to the Sponsor and entered in the EDC within 24 hours of the knowledge.

12. STUDY MANAGEMENT

12.1. Sponsor Responsibilities

As the Sponsor of this clinical study, Applaud Medical has the overall responsibility for the conduct of the study, including assurance that the study meets US federal and local regulatory requirements appropriate to the conduct of the study. In this study, Applaud will have certain direct responsibilities and might delegate other responsibilities to a Contract Research Organization (CRO). The study sponsor will adhere to sponsor general duties as described in ISO 14155:2020, Clinical investigation of medical devices for human subjects – Good clinical practice, and CFR Part 812, 50, 56, 54 and the World Medical Association Declaration of Helsinki.

General Duties

Applaud will ensure that the application is submitted to the appropriate regulatory authorities, obtaining copies of IRB approvals, and ensuring documentation of IRB approvals prior to the shipment of devices, ensuring proper clinical site monitoring, ensuring subject informed consent is obtained, providing quality data that satisfies regulations and informing the Investigators and IRBs of unanticipated adverse device effects, adverse events, and deviations from the protocol as appropriate.

The investigation must be reviewed and approved by the appropriate IRBs before subject enrollment may begin. All proposed changes to the clinical study must be reviewed and approved by Applaud. Applaud will also obtain any necessary regulatory approval, per local requirements.

Selection of Clinical Sites

The primary requirements of site and Investigator selection and continued participation in the study are: adequate experience, commitment to safety, consistency in adherence to the protocol, and subject volume. Participating sites will be screened to ensure they have sufficient numbers of eligible subjects who are representative of the target population. Each center must have facilities that are capable of processing subjects in the manner prescribed by the protocol.

The study sponsor, Applaud, and its designees will select qualified Investigators, ship or deliver devices only to participating Investigators, obtain signed study agreements, and provide Investigators with the information necessary to conduct the study.

Site Training

The training of appropriate clinical site personnel will be the responsibility of the Sponsor or designee. The Investigator is responsible for ensuring that his/her staff conduct the study according to the protocol. To ensure proper device usage, uniform data collection, and protocol compliance, the Sponsor or designee will present a formal training session to study site personnel which will review the instructions for use of the device, the Clinical Study Protocol, instructions on in-hospital data collection, methods for soliciting data from alternative sources, schedules for follow-up with the study site coordinators, and regulatory

CONFIDENTIAL Page 40 of 53 requirements. Detailed feedback regarding completion of forms will be provided by the Sponsor or designee through the regular site monitoring.

Investigator Training

The Sponsor will provide appropriate Investigator training on the technique via the IFU. Each investigator will be trained to the Acoustic Enhancer by the Sponsor prior to treating the first subject. Training will be documented for each investigator as outlined in the IFU.

Subject Confidentiality

Subject confidentiality will be maintained throughout the clinical study in a way that ensures the information can always be tracked back to the source data. For this purpose, a unique subject identification code (ID number and subject name code) will be used that allows identification of all data reported for each subject.

Data relating to the study might be made available to third parties (for example in case of an audit performed by regulatory authorities) provided the data are treated confidentially and that the subject's privacy is guaranteed. As part of the informed consent process, the subject is informed that their medical chart will be reviewed by the Sponsor and its designates, and by government regulatory authorities. Each study site is responsible for ensuring it has in place appropriate policies and procedures to maintain subject confidentiality according to applicable laws, including without limitation, the Health Insurance Portability and Accountability Act (HIPAA) and any applicable state laws. It is also the investigator's responsibility to obtain written authorization from each study subject in compliance with applicable laws allowing the disclosure of all study results described in the protocol before the subject is entered into the study.

Data Management

Applaud or a representative of the Sponsor will be responsible for database creation and validation. Prior to finalizing and locking the database, all decisions concerning the inclusion or exclusion of data from the analysis for each subject will be determined by appropriate clinical and statistical personnel. Any and all exclusions related to either safety or efficacy will be documented in subject listings.

Record Retention

Applaud will maintain copies of correspondence, data, shipment of devices, adverse device effects, Investigator agreements and other records related to the clinical trial. All study records and reports will remain on file at the sites for a minimum of 2 years after completion of the Study, and will further be retained in accordance with local guidelines as identified in the clinical study agreement. Study records are to be discarded only upon notification by the study sponsor. The Investigator must contact the study sponsor before the destruction of any records and reports pertaining to the study to ensure they no longer need to be retained. In addition, the sponsor should be contacted if the Investigator plans to leave the investigational site. All required data for this study will be collected on standardized CRFs or an electronic data capture system. All information and data sent to the Sponsor or Contract Research Organizations (CROs) concerning subjects or their participation in this study will be considered confidential. All data used in the analysis and reporting of this evaluation will be used in a manner without identifiable reference to the subject. The Principal Investigator consents to visits by the staff of the Sponsor and its authorized representatives and the U.S. Food and Drug Administration or any other local governmental body to review the study subjects' medical records including any test or laboratory data that might have been recorded on diagnostic tests media (e.g., CT scans, X-rays, etc.).

CONFIDENTIAL Page 41 of 53

12.2. Investigator Responsibilities

The Investigator shall ensure that all work and services described herein, or incidental to those described herein, shall be conducted in accordance with the highest standards of medical and clinical research practice. The Investigator will provide current copies of the study protocol to all Sub- Investigators or other site personnel responsible for study conduct. The investigator should follow the clinical study in accordance with the Acoustic Enhancer Research on Laser Lithotripsy Clinical Study Investigator's Agreement (CLIN-0004).

Upon completion or termination of the study, the Investigator will submit a final written report to the study sponsor and the reviewing IRB. The report should be submitted to the study sponsor within three (3) months of study completion or termination. The Investigator will provide the study sponsor or designee with copies of all IRB actions regarding the study.

IRB Approval and Informed Consent

The investigation must be reviewed and approved by the appropriate IRBs before subject screening may begin. All proposed changes to the investigational plan must be reviewed and approved by the Sponsor. Prior to shipment of study devices, a signed copy of the IRB Committee approval letter identifying the clinical study must be submitted to the Sponsor signifying study approval. Investigators are responsible for obtaining and maintaining approval of the study by the IRB.

Written informed consent is mandatory and must be obtained from all subjects prior to performing any study procedures in this clinical study. Applaud Medical will provide each Investigator site with a Sponsor approved consent template. Each site is expected to modify the template, if necessary, to meet their facilities requirements. Modified ICF templates must be reviewed by the Sponsor prior to submission to their IRB.

Informed consent must be obtained and shall inform the subject as to the objective and procedures of the study and possible risks involved. The subjects must be informed about their right to withdraw from the study at any time and for any reason without sanction, penalty, or loss of benefits to which the subject is otherwise entitled and that withdrawal from the study will not jeopardize their future medical care. The clinical study informed consent must be used in addition to the institution's standard consent form for urological surgery. The institutional standard subject consent form does not replace the study consent form.

It is the responsibility of the Investigator to obtain both an authorization for subject health information and study consent. The IRB approved Informed Consent Forms must be retained at the investigational site along with the other investigational case report forms. A copy of the consent form must be given to each subject enrolled in the study.

Data Collection and Reporting

Electronic Case report forms (eCRFs) will be used to record demographic, procedural, and follow-up data, as well as any unscheduled visits or adverse clinical events which may occur during the study period. The AEs and incidence of morbidity and mortality will be reviewed with the Investigators to assess the safety of the device and the procedure.

Qualified study staff at each clinical site will perform primary data collection drawn from sourcedocument (hospital chart) reviews. The Monitor will perform clinical monitoring, including review of CRFs with verification of study eligibility, informed consent process, scheduled and unscheduled follow-up visits and AEs to the source documentation.

CONFIDENTIAL Page 42 of 53

Data Completion and Submission

Investigators, or delegated site personnel, should complete CRFs within the EDC system in a timely fashion, preferably within 10 business days after subject enrollment or follow-up visit. This will enable timely monitoring visits.

Serious adverse events should be reported within 24 hours of first knowledge of the event.

Device Accountability

The Investigator shall maintain adequate records of the receipt and disposition of all study devices. When the enrollment is complete, the Investigator shall return any unused devices to the study sponsor. The Device Accountability Log shall document quantity of device (lot number) received, used and any unused devices that have been returned to the Sponsor, or otherwise disposed of.

Source Documents

The Investigator shall maintain accurate, complete, and current records relating to the Investigator's participation in an investigation including records of each subject's case history and exposure to the device. Case histories include the case report forms and supporting data including, for example, signed and dated consent forms and medical records including, progress notes of the physician, the individual's hospital chart(s), and the nurses' notes. Such records shall include:

- Documents, evidencing the informed consent process and, for any use of a device by the Investigator without informed consent, any written concurrence of a licensed physician and a brief description of the circumstances justifying the failure to obtain informed consent. The case history for each individual shall document that informed consent was obtained prior to participation in the study. All relevant observations, including records concerning adverse device effects (whether anticipated or unanticipated), information and data on the condition of each subject upon entering, and during the course of, the investigation, including information about relevant previous medical history and the results of all diagnostictests.
- A record of the exposure of each subject to the investigational device, including the date and time of each use, and any other therapy.

Regulatory Filing

The following records must be maintained in designated study administrative files:

- Clinical Protocol and all amendments
- Signed Investigator Agreement
- IRB approval letter(s) and approved Informed Consent(s) (including any revisions)
- Correspondence relating to this study (with Sponsor, Monitors, other Investigators, etc.)
- Correspondence with the IRB
- Instructions for Use
- Curriculum Vitae for all Investigators
- Device log
- Device related paperwork (including shipping and return documentation, including packing slips)
- Site Visit Log
- Delegation of Authority Log
- Blank set of CRFs and instructions for completion
- Reports (including Adverse Event reports, annual reports and final reports from Investigator and Sponsor)

The following records must be maintained for each subject enrolled in the study:

- Signed subject Informed Consent Form
- All completed CRFs
- Record of any side effects/adverse events and treatment failures (with supporting documentation)
- Procedure reports, physician dictations, nursing notes, and subject medical records
- Copies of all subject X-rays, CT Scans and ultrasounds where applicable
- Records of any interventions (procedure reports, physician dictations, nursing notes, etc.)
- Records related to subject deaths during the investigation (including death records, death certificate and autopsy report, if performed)

Investigator files containing all records and reports of the investigation should be retained for a minimum of 2 years after the completion or termination of the investigational study or until 2 years after they are no longer needed to support product approval. They may be discarded upon notification by the Sponsor. To avoid any error, the Investigator should contact the Sponsor before destroying any records and reports pertaining to the study to ensure they no longer need to be retained.

Audits/Inspections

In the event that audits are initiated by the Sponsor (or its designate), or national/international regulatory authorities, the Investigator shall allow access to the original medical records and provide all requested information.

